# 8.1.2 Secondary study parameters/endpoints (if applicable)

Secondary analyses are aimed at defining the ability of the MMC to accurately identify patients at risk for a drug-drug-gene interaction. The effect of integrating the MMC into healthcare on the incidence of adverse drug events compared to matched historical controls from the U-PGx cohort will also be assessed.

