**Intervention**: The MMC that provides patient centred information on drug-drug interactions and pharmacogenetics affecting personal polytherapy. The MMC will show a selection of high quality publicly available information such as details on different types of medications, including their uses, side effects and instructions for use, in the language of the patient. This information is targeted at an individual patient's medication profile to inform patients to better understand and deal with their personal health information, with regard to drug therapy. Patients in the Netherlands, Slovenia and Greece also will receive their PGx profile to further personalise the MMC experience.

**Main study parameters/endpoints**: The primary outcome is the sense of empowerment and health literacy for participants before and after use of the MMC. Secondary outcomes include an evaluation of the drug-drug-gene interactions and adverse drug events in the study populations compared to matched historical controls.

Nature and extent of the burden and risks associated with participation, benefit, and group relatedness: Patients are exposed to the regular treatment. In addition, patients will receive questionnaires at baseline, two, and twelve weeks regarding the use and experience of the medication management centre, and a close-out interview at week twelve. In addition, 10ml of blood will be collected during a venipuncture for pharmacogenetic analyses.

Benefits include having access to the medication management centre for the duration of the study. Additionally, patients will receive their PGx profile. This can be used to individualize drug treatment, based on the Dutch Pharmacogenetics Working Group (DPWG) guidelines.

Overall, minimal risks are expected for subjects as they will receive normal clinical care. Information from the MMC will be a curation of existing publicly available data. Any information regarding DDIs and DGIs will be supplemented with a disclaimer that the patient should not adjust their treatment without talking to a healthcare provider.

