# 2.2 Secondary objective

To investigate if the medication management centre is able to identify patients at risk for a drug-drug-gene interaction. Moreover, it will be investigated whether integrating the MMC into healthcare will lower the adverse drug event rate compared with matched historical control.

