Effectiveness in the prevention of ADRs and the ability to identify drug-drug-gene interactions will be explored as a secondary endpoint by comparing results of the pilot study with those obtained from matched historical controls obtained from the control arm of the U-PGx project. This control arm is suitable as historical control group for the EmPaSafe study because of its alignment in key aspects, allowing for meaningful comparisons:

- Genotyped but not empowered with PGx Data: Participants in the U-PGx control arm were genotyped retrospectively, meaning their PGx information was available but not actively utilized in their care. This setup provides a unique baseline to assess the effectiveness of the MMC and the empowerment of EmPaSafe patients with PGx data, as we can analyse whether access to their genetic information and medication adjustments reduces ADRs and improves drug efficacy.
- Comparable Follow-up and Monitoring Protocols: The U-PGx control arm and the EmPaSafe study share similar follow-up methods, including regular monitoring for ADRs and the use of similar questionnaires. This similarity minimizes variation in data collection processes, allowing us to more directly compare ADR prevalence and other outcomes between the two groups.
- Matching for Key Variables: The control group will be matched to EmPaSafe participants based on age, sex, and type and number of medications, controlling for these variables in the analysis. This matching enhances the comparability of the two cohorts and strengthens the reliability of conclusions drawn about the impact of empowering patients with PGx data through the MMC.

Using the U-PGx control arm as a historical comparison thus allows EmPaSafe to evaluate the added value of PGx-informed care without needing a concurrent control group, streamlining the study while leveraging pre-existing data to explore the MMC's role in improving medication safety and personalization.

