### Secondary clinical outcome:

- Total number of ADEs (related to index and subsequent drugs)
- Dose adjustments to index drug
- Drug cessation (and reason for discontinuation)
- Additional drugs that are prescribed during follow-up
- Routine drug levels (only those that are collected routinely) as a proxy for exposure
- Patient-reported drug adherence

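### The aim of showing that the MMC accurately identifies drug-drug-gene interaction risk is paired with a historical-control comparison that, as written, does not measure accuracy

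*Protocol*

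**What the plan says.** Three places in the Protocol state the identification aim or its method.

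- **Objective (Section 2.2).** "To investigate if the medication management centre is able to identify patients at risk for a drug-drug-gene interaction". No comparator and no reference classification is named here.
- **Endpoint (Section 8.1.2).** "Secondary analyses are aimed at defining the ability of the MMC to accurately identify patients at risk for a drug-drug-gene interaction". This is the only place where accuracy enters. The sentence that follows it attaches the control comparison to a different outcome: the effect of the MMC "on the incidence of adverse drug events compared to matched historical controls from the U-PGx cohort will also be assessed".
- **Method (Section 3.1).** "the ability to identify drug-drug-gene interactions will be explored as a secondary endpoint by comparing results of the pilot study". The comparator is a matched historical group drawn from the U-PGx control arm. The same sentence also covers prevention of adverse drug reactions. The Summary joins the two again: "Secondary outcomes include an evaluation of the drug-drug-gene interactions and adverse drug events in the study populations compared to matched historical controls".

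On the controls, Section 3.1 says: "Participants in the U-PGx control arm were genotyped retrospectively, meaning their PGx information was available but not actively utilized in their care". No MMC output is described for them. The six items listed under secondary clinical outcomes in Section 8.1.2 do not include an interaction flag, and Section 10.2 provides for descriptive statistics only. Section 8.2 says that the German patients use the MMC without PGx testing.

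**The concern.** To say that a tool identifies at-risk patients accurately, one needs a two-way table of flag against true status in the same patients. Section 3.1 instead offers a contrast between MMC users and other people from an earlier cohort. That contrast can show whether interactions or adverse events are more or less frequent in one cohort than in the other. It does not show whether the flags fell on the right patients.

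The first secondary objective is at stake. If interactions turn out about equally common in both cohorts, the result could be reported as evidence that the MMC finds the patients it should find, although the same result is compatible with a tool that flags at random. A lower adverse event rate than in the controls would concern the effect of the MMC, which is a separate question.

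**Working it through.** The Protocol gives no accuracy figure, power or error rate for this endpoint, so there is no stated result to reproduce. The only figure to check is the sample size: 4 sites × 30 = 120 (Section 3.1), which agrees.

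**Step 1: who can be flagged.** The German site does not genotype (Sections 3.1 and 8.2). Genotyped patients: 3 × 30 = 90. For the other 30, the drug-drug part of the MMC is available and the gene part is not.

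**Step 2: what a frequency comparison can show.** Let π be the proportion truly at risk, Se the sensitivity and Sp the specificity. The proportion flagged is

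q = Se × π + (1 − Sp) × (1 − π).

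Give the comparison its best case: the matched controls reveal π exactly, the pilot gives q, and the two agree. Assume π = 0.30 and q = 0.30; the documents state neither.

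| Tool | Se | Sp | q | Youden index (Se + Sp − 1) |
|---|---|---|---|---|
| Perfect | 1 | 1 | 1 × 0.30 + 0 × 0.70 = 0.30 | 1 |
| Intermediate | 0.50 | 0.786 | 0.50 × 0.30 + 0.214 × 0.70 = 0.30 | 0.29 |
| Chance level | 0.30 | 0.70 | 0.30 × 0.30 + 0.30 × 0.70 = 0.30 | 0 |

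All three produce the same pair of frequencies. There is one equation and two unknowns (Se and Sp), so frequencies alone do not settle accuracy. The example does not hang on 30%: at π = q = 0.10 a chance-level tool (Se 0.10, Sp 0.90) gives 0.10 × 0.10 + 0.10 × 0.90 = 0.10, and at π = q = 0.50 (Se 0.50, Sp 0.50) it gives 0.50. Both again match the perfect tool.

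**Step 3: what the study can report.** The proportion flagged among the 90 can be estimated directly. The Wilson 95% interval, with z = 1.96, is

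[p + z²/(2n) ± z × √(p(1 − p)/n + z²/(4n²))] / (1 + z²/n).

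For n = 90 and assumed counts:

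| Flagged | Proportion | 95% CI |
|---|---|---|
| 9 of 90 | 10% | 5% to 18% |
| 27 of 90 | 30% | 22% to 40% |
| 45 of 90 | 50% | 40% to 60% |

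That is adequate for a descriptive statement in a proof-of-concept study.

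**The case against.** The best reply has four parts.

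1. *Section 8.1.2 does not itself name the control comparison for identification.* Correct. The link comes from Section 3.1 and the Summary, and those are the places to change first. They still give the only stated method, and they contradict the separation that Section 8.1.2 makes.

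2. *Reference standard, flag definition and estimators belong in a statistical analysis plan.* This holds for the details, and their absence is not the point here. The pairing of an accuracy aim with a between-cohort comparison, however, is made in the Protocol itself.

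3. *The controls are genotyped, so the MMC rules could be applied to their records.* Also fair. A reader might infer that the U-PGx controls can never contribute anything on accuracy; the documents do not support that. They leave such a step open without stating it. That the controls did not use the MMC is likewise an inference, drawn from their being historical and the MMC being newly developed.

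4. *The endpoint is exploratory and nothing is powered (Section 4.4).* This excuses imprecision and lowers the severity. It does not turn a cohort difference into an accuracy measure.

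Two further readings are tempting and should be left out. One is that pilot patients who act on a flag spoil their later events as a reference; the Protocol nowhere proposes later events as the reference for identification. The other is that enrolling German patients is an error; Section 3.1 discloses that they have no PGx data and explains what they contribute beyond it.

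**Conclusion.** The concern holds in a limited form. As written, the comparison in Section 3.1 and the Summary would not support a conclusion that the MMC identifies at-risk patients accurately, because identical cohort frequencies are compatible with anything from perfect to chance-level classification. Any drug-drug-gene result can rest on at most 90 of the 120 patients. The 30% prevalence and flag rate are assumptions chosen for illustration; the failure to identify sensitivity and specificity from frequencies does not depend on them.

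The issue is minor to moderate. The endpoint is secondary, exploratory and descriptive, and neither the primary endpoint nor the comparison of adverse drug events with controls is touched by this point.

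**What to change.** 1. In Section 8.1.2, drop the word *accurately*. Align Sections 2.2 and 3.1 and the Summary, so that the aim is to describe how many patients the MMC flags for a drug-drug-gene interaction.
2. In Section 3.1 and the Summary, separate identification from the historical-control comparison, and keep that comparison for the incidence of adverse drug events only.
3. Report the number and proportion flagged among the 90 genotyped patients, with a 95% CI. What counts as a flag can be defined in the statistical analysis plan.
4. Optional, if the control medication records allow it: run the locked MMC rules offline on the genotyped U-PGx controls, and report the frequency of adverse drug events in flagged and unflagged controls. Label this as association with adverse drug events. It should not be called sensitivity or specificity for interaction risk, because adverse events have many causes and many at-risk patients will have none.

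Items 1 to 3 need a wording change and one simple table; Section 3.3 says that the MMC already collects its own interaction assessments. Item 4 adds some analysis work, and the documents do not show whether the control records are complete enough for it. The price is a more modest secondary claim.

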# Baseline demographics and clinical monitoring:

- Demographic measurements
- Current and past medical history
- Comorbidities
- Global Health Score
- Co-medication
- Renal function
- Liver function

### Secondary clinical outcome:

- Total number of ADEs (related to index and subsequent drugs)
- Dose adjustments to index drug
- Drug cessation (and reason for discontinuation)
- Additional drugs that are prescribed during follow-up
- Routine drug levels (only those that are collected routinely) as a proxy for exposure
- Patient-reported drug adherence

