# 3. STUDY DESIGN

## 3.1 Overall study design

This study is a multi-centre, open-label study to assess the impact of the developed MMC in combination with the developed risk score algorithms, patient-reported outcome tool, and model-based precision dosing tool on patient empowerment of polypharmacy patients, thereby improving drug safety. In the study, a total of 120 patients will be enrolled in The Netherlands, Greece, Slovenia, and Germany (30 patients per country). The study subjects will be followed for 12 weeks. At set time intervals (2 and 12 weeks) the subjects will be asked to complete a validated questionnaire through the eClinical Data Management Platform Castor (table 1), for which the patients receive an email and a reminder through the MMC. These questionnaires collect information on the experience with the MMC, clinical monitoring, clinical outcome, and adverse events.

Table 1. Overview of the questionnaires during the 12-week follow-up. The baseline questionnaire comprises of 97 questions, the 2-week questionnaire of 133 questions and the 12-week questionnaire of 206 questions. All questionnaires are adaptive.

	Baseline questionnaire	Adaptive questionnaire in the MMC at time point:	
		2 weeks	12 weeks
Experience			
Usability		Х	х
Health literacy	х		х
Clinical monitoring			
Comorbidities and allergies	х		
Concurrent medication and herbal	х	х	х
remedies (through patient diary)			
Clinical outcome			
Drug adherence	х	Х	х
Quality of Life	х		х
Adverse events			
Patient reported ADR		Х	х
Assessment of ADR severity		х	х
Pharmacogenomics			
DNA sample collection	Х		

The baseline questionnaire will additionally comprise questions covering in- and exclusion criteria, demographics, recruitment information, previous PGx test results, comorbidities and allergies, and the level of health literacy before use of the MMC. In total, the baseline questionnaire consists of 97 questions. The questionnaire offered two weeks after inclusion in the study consists of 133 questions. The last questionnaire, offered 12 weeks after inclusion in the study, consist of 206 questions. All questionnaires are adaptive meaning that the length and duration of the questionnaire depends on the answers of the participants.

[figure not shown]

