# 4.4 Sample size calculation

As this is a proof-of-concept (PoC) pilot study, the sample size is aimed at showing the impact of the use of the MMC on patient empowerment and exploring associations, rather than statistically significant relations. Therefore, no formal sample size and power calculation is done. A number of 30 participants per site is the number of subjects that we estimate to be sufficient to investigate the impact of using the medication management centre and associated tools.

To explore potential effectiveness of the tool, results will be compared with those of matched historical controls obtained from the control arm of the U-PGx project. While the study is not aimed at or powered for statistical comparisons, we are in the unique position to have a access to a substantial cohort of comparable patients. Controls will be matched for age, sex and type and number of mediations. These results will help to design a larger study to perform a formal statistical analysis of the effect of the medication management system and associated tools.

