# 5.1.2 Questionnaires

The baseline questionnaire will comprise questions regarding demographics, in- and exclusion criteria, and comorbidities. Additionally, standardized questionnaires will be offered to the patients at 2 and 12 weeks after initiation of the index drug to obtain information about health behaviour, drug use, ADRs (PRO-CTCAE), quality of life (SF-36), MMC experience and health literacy (HLS-EU-Q47). The questionnaires are adaptive meaning that based on the provided answers only relevant follow-up questions will be asked to minimize the burden. Lastly, a semi-structured close-out interview will be held at week 12 to gather information on the experience with the MMC.

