## **10.2 Secondary study parameter(s)**

Descriptive statistics will be used to describe the secondary outcomes.

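### ADR severity is collected at weeks 2 and 12, but the ADE outcome is a severity-blind total, so the descriptive comparison with historical controls can mask or run opposite to a change in severe ADEs

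*Protocol*

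**What the plan says.** **What is collected.** Table 1 in section 3.1 has two adverse-event rows, one for the patient-reported ADR and one for "Assessment of ADR severity". Both are marked at weeks 2 and 12. Section 5.1.2 lists the questionnaire content as including "drug use, ADRs (PRO-CTCAE), quality of life (SF-36), MMC experience and health literacy (HLS-EU-Q47").

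**What is made an outcome.** Among the secondary clinical outcomes in 8.1.2, the single ADE item is "Total number of ADEs (related to index and subsequent drugs"). No item in that list mentions grade, severity or seriousness.

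**What is compared.** Section 2.2 asks whether "integrating the MMC into healthcare will lower the adverse drug event rate compared with matched historical control". Section 8.1.2 says that the "incidence of adverse drug events compared to matched historical controls from the U-PGx cohort will also be assessed". Section 3.1 justifies the U-PGx control arm partly as "allowing us to more directly compare ADR prevalence and other outcomes between the two groups". None of these three mentions severity.

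**How it is analysed.** Section 10.2 says: "Descriptive statistics will be used to describe the secondary outcomes". Section 4.4 says: "Therefore, no formal sample size and power calculation is done".

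**The concern.** Severity is asked of patients at both follow-up questionnaires, yet no objective, outcome or analysis sentence uses it. The drug-safety result is a sum in which a mild symptom and a severe reaction count the same.

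That matters more here than in most studies, because the intervention can change reporting. The MMC shows patients the side effects of their own drugs (Summary, Intervention), lets them record ADRs in a diary (3.2), provides tools for reporting health concerns (5.1.1) and is the channel through which AEs are monitored (9.2.1). The controls come from an earlier project and did not have it. Better awareness and an easier channel could plausibly raise the number of mild reports, while the hoped-for benefit, fewer harmful interactions, would be expected to show mainly in the more severe reactions. A single total adds the two together.

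At stake is how the descriptive comparison is read. Section 4.4 intends these results to help design a larger study, so a measure that points the wrong way could be carried forward.

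**Working it through.** **No figure to reproduce.** The protocol gives no ADE rate, severity split, effect size, alpha or power for this outcome. The only related arithmetic, 4 sites × 30 = 120, agrees with the stated total. The check therefore has two parts.

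**1. Is severity used anywhere?**

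| Place | Measure | Severity used? |
|---|---|---|
| 3.1, Table 1 | ADR report and ADR severity, weeks 2 and 12 | Collected |
| 5.1.2 | PRO-CTCAE | Instrument named |
| 2.2 | Rate of ADEs | No |
| 3.1, control-arm rationale | Prevalence of ADRs | No |
| 8.1.2, opening text | Incidence of ADEs | No |
| 8.1.2, outcome list | Total number of ADEs | No |
| 10.2 | Descriptive statistics | No |
| 9.2.2 | SAE definition and reporting | Seriousness only; not an outcome compared with controls |

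Severity is collected and then not used. The measure is also worded in four ways (rate, prevalence, incidence, total), all of them severity-blind.

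**2. Can a total move against severe ADEs?** Let

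- *s* = severe share of control ADEs,
- *R* = ratio of severe ADEs, MMC to control,
- *Q* = ratio of non-severe ADEs, MMC to control.

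With equal exposure, the ratio of totals is *T* = *sR* + (1 − *s*)*Q*. All three inputs are assumptions, and *s* is varied from 5% to 20%.

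*Severe ADEs halve, non-severe reports rise 20% (R = 0.5, Q = 1.2):*
- s = 5%: 0.05 × 0.5 + 0.95 × 1.2 = 1.165
- s = 10%: 0.10 × 0.5 + 0.90 × 1.2 = 1.130
- s = 20%: 0.20 × 0.5 + 0.80 × 1.2 = 1.060

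The total worsens across the whole range although severe ADEs halved.

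*Severe ADEs double, non-severe ADEs fall 20% (R = 2.0, Q = 0.8):*
- s = 5%: 0.05 × 2 + 0.95 × 0.8 = 0.860
- s = 10%: 0.10 × 2 + 0.90 × 0.8 = 0.920
- s = 20%: 0.20 × 2 + 0.80 × 0.8 = 1.040

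The direction is reversed at 5% and 10%. At 20% it is right, but the doubling is almost hidden.

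*Break-even:* the total is unchanged when *Q* = (1 − *sR*)/(1 − *s*). With R = 2 this gives 0.90/0.95 = 0.947, 0.80/0.90 = 0.889 and 0.60/0.80 = 0.750. A doubling of severe ADEs is thus cancelled by a fall in non-severe ADEs of about 5%, 11% or 25%.

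The formula is for event counts. It does not carry over directly to a patient-level prevalence, where a patient counts once however many mild events are added. That measure is still severity-blind, but the sizes above would not apply to it.

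**The case against.** **It is SAP detail.** Tabulating a collected variable by grade is ordinary SAP content, and nothing in 10.2 forbids it. This stands for layout. It does not dispose of the point, because 8.1.2 itself states the ADE outcome, and states it as a total.

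**Severe harm is already captured.** A reader might infer from the outcome list that severe harm goes unseen. The protocol does not support that. SAEs are defined and reported (9.2.2) and enter the annual progress report (12.4), and 8.1.2 lists drug cessation with its reason and dose adjustments. These capture part of severe harm. But SAEs are not named as an outcome compared with the controls, and seriousness is not severity: a severe reaction may meet no seriousness criterion.

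**The figures are assumed and the fix is imprecise.** Both are true. The protocol suggests no mechanism for severe ADEs doubling while mild ones fall; the opposite pattern is the plausible one. Precision is poor as well. With 100 control ADEs, 10 of them severe, halving the severe ones and adding 10% to the rest gives 90 × 1.10 + 5 = 104. Treating counts as Poisson with equal exposure, 104 against 100 is a ratio of 1.04 (95% interval about 0.79 to 1.37), and 5 against 10 severe events is 0.50 (about 0.17 to 1.46). Neither is clear alone. The severe row still tells a reader that the two parts of the total may be moving apart.

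**The mechanism is differential ascertainment.** Severity grades come from the same self-reporting patients, so grading lessens that problem without curing it. This stands.

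**Control severity data are unknown.** Section 3.1 says only that the questionnaires were similar. This stands, and the fix has to allow for it.

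**Conclusion.** The point holds as one of outcome definition. Severity is collected at both follow-up questionnaires, the ADE outcome is a total, and no other wording of the comparison brings severity in. A total dominated by mild self-reports, which the MMC may itself increase, can mask or run opposite to a change in severe ADEs.

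The size cannot be known from the protocol. The illustrative totals of 1.06 to 1.17 and 0.86 to 1.04 rest wholly on the assumed severe share, the assumed ratios and equal exposure. They show that reversal is possible, not that it is likely.

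A reader might go further and infer that the trial would answer its main safety question wrongly. The protocol does not support that. The primary endpoint is empowerment and health literacy (8.1.1). The ADE comparison is secondary, exploratory, unpowered and descriptive, and no test or success rule depends on the total. The consequence is a descriptive result that may be misread and carried into the design of a larger study. Because the correction needs no new patient data, it is worth making.

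**What to change.** In 8.1.2:

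1. Keep the total number of ADEs.
2. Add, from the severity items already collected, the number and proportion of patients by worst ADE severity, including those with at least one severe ADE.
3. Show serious ADEs separately, using the seriousness definition in 9.2.2.
4. Make the U-PGx comparison at the same severity level where the control data hold comparable grades. Where they do not, report severity within EmPaSafe only, and state that the comparison with controls is severity-blind.
5. Use one term for the compared measure in 2.2, 3.1 and 8.1.2.

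**Cost.** Outcome wording and a few table rows, plus a check of what the U-PGx data hold. There is no new questionnaire item and no change to the sample size. The severe rows will have few events and be imprecise, and self-reported grades will not remove differential reporting against the controls; both limits should be stated beside the table. This changes an outcome definition and touches no rule of clinical management.
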